8.2.3 Secondary Analyses

A per-protocol analysis will compare randomized groups among protocol adherent patients – here, defined among as those actually receiving the procedure and making $\geq 80\%$ follow-up visit in both groups. Modified ITT will be considered the primary approach for all efficacy analyses and will include patients who actually received the intervention regardless of adherence to follow-up visits. Safety endpoints and adverse events may be evaluated based on treated group (per-protocol).

Additional outcomes and analyses not specified here are considered exploratory and post-hoc and will be clearly identified as such in any publications.

^b %TBWL defined as $[(\text{pre-operative weight} - \text{post-operative weight}) / (\text{pre-operative weight})] \times 100$

^c % EWL defined as $[(\text{pre-op weight} - \text{follow up weight}) / (\text{pre-op weight} - \text{ideal body weight})] \times 100$

Note: "Ideal body weight" of BMI 25

Missing Data

The primary analysis uses a hierarchical regression model, assuming post-randomization dropout is missing at random (MAR) among subjects completing at least 1 of the planned follow up visits.

Patients excluded after randomization and before intervention on the basis of identified exclusion criteria will be excluded from analyses; reasons for meeting exclusion criteria will be documented. Patients that withdraw/dropout between randomization and intervention are assumed to be missing completely at random. However, a sensitivity analysis will compare withdrawn subjects to participating subjects and perform analyses under MAR (including multiple imputation) assumptions if these subjects appear different or if dropout occurs at substantially different rate in one arm compared to the other. Participating patients who dropout prior to the first follow up visit will be analyzed similarly.

Randomization and Data Collection

Stratified block randomization schedules will be uploaded to REDCap. Data will be collected in REDCap data collection forms.

Interim Analysis

No interim analysis will be performed for efficacy endpoints. Adverse events will be monitored throughout and discussed with the data monitoring committee.

ETHICAL CONSIDERATIONS

This study is to be conducted according to United States government regulations and Institutional research policies and procedures.

This protocol and any amendments will be submitted to a properly constituted local Institutional Review Board (IRB), in agreement with local legal prescriptions, for formal approval of the study. The decision of the IRB concerning the conduct of the study will be made in writing to the sponsor-investigator before commencement of this study.

All subjects for this study will be provided a consent form describing this study and providing sufficient information for subjects to make an informed decision about their participation in this study. This consent form will be submitted with the protocol for review and approval by the IRB for the study. The formal consent of a subject, using the Approved IRB consent form, must be obtained before that subject undergoes any study procedure. The consent form must be signed and dated by the subject or the subject's legally authorized representative, and the individual obtaining the informed consent.

STUDY FINANCES

Funding Source

The study is financed through the funding partner, Erbe Elektromedizin GmbH, and the Mayo Clinic Rochester.

Conflict of Interest

Any study team member who has a conflict of interest with this study (patent ownership, royalties, or financial gain greater than the minimum allowable by their institution, etc.) must have the conflict reviewed by a properly constituted Conflict of Interest Committee with a Committee-sanctioned conflict management plan that has been reviewed and approved by the study sponsor-investigator prior to participation in this study.

Subject Stipends or Payments

Subjects will not receive remuneration for taking part in this study.

The procedure costs and all other costs associated with imaging, testing, procedure day, and follow-up visits will be covered by the funding partner, Erbe Elektromedizin GmbH, and Mayo clinic Rochester. Subjects will not pay for any procedure or test performed as part of the study and outlined in the protocol.

REFERENCES

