Twenty-four eligible participants will be block-randomized 1 to 1 treatment (12 participants) and control (12 participants) groups. All participants will undergo endoscopy and those without endoscopic contraindications will be eligible. All treatment group subjects will undergo combined HAPC and ESG where APC is applied according to on-label use prior to the standard ESG technique for enhanced fibrosis along the site of the plications potentially providing an avenue for longer and more durable ESG while minimizing the associated complications. Control subjects will undergo traditional ESG alone. All participants will undergo a repeat upper endoscopy at 26 weeks (6 months) +/- 2 weeks to evaluate the durability of the endoscopic sutures. All subjects will undergo research MRI at baseline and 26 weeks +/- 2 weeks to evaluate and grade the durability of the created gastroplasty, gastric motility, and gastric accommodation. This specially developed MRI protocol at Mayo offers a gold standard in evaluating gastroplasty durability. Additionally, at both baseline and 26 weeks +/- 2 weeks, all patients will undergo gastric scintigraphy to evaluate and measure gastric emptying.

Endpoints Effectiveness

Primary:

- Assess durability of endoscopic plications and sutures 26 weeks (6 months) +/- 2 weeks post procedure between patients receiving HAPC/ ESG vs traditional ESG alone.

Secondary:

- %TBWL in the combined HAPC and ESG group compared to traditional ESG at 6 and 12 months.
- Assess the procedure safety.
- % Excess weight loss (EWL) at 6 and 12 months between both groups.
- Proportion with $\geq 25\%$ EWL at 6 and 12 months by randomized arm.
- % of patients in the combined HAPC and ESG group achieving $\geq 5\%$ TBWL at 6 and 12 months compared to ESG alone.
- % of patients in the combined HAPC and ESG group achieving $\geq 10\%$ TBWL at 6 and 12 months compared to ESG alone.
- Changes in quality of life assessed using standard validated questionnaires (IWQOL-lite and SF-36) at 6 and 12 months compared to baseline.
- Changes in depression assessed using PHQ-9 questionnaire at 6 and 12 months compared to baseline.

- Improvement/reduction of hunger and desire to eat evaluated using validated self-reported ratings of appetite based on a 100-mm visual-analogue scale at 6 and 12 months compared to baseline.
- Improvement in eating behaviors evaluated using the Three Factor Eating Questionnaire (TFEQ) at 6 and 12 months compared to baseline.

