Patients withdrawn prior to undergoing combined HAPC and ESG or ESG alone will count towards the target accrual. Screen failed patients will not count towards target accrual. New patients will be randomized to target accrual of 24 total patients receiving combined HAPC and ESG or ESG alone. The power and sample size calculation includes sufficient patients to yield power assuming some post-intervention dropout.

Source Documentation

Study source worksheets and/or electronic documentation in the medical record will be used as source documentation for the trial for all participant follow-up visits. Source documentation from the electronic medical record will be required for the procedure(s), medications, and any serious adverse medical events. REDCap will be used for collection of electronic sources and verified by PI attestation as the eCRF. If unavailable to conduct electronic source, physical CRF source worksheets will be available and can be added to the eCRF for investigator attestation.

PROTOCOLS FOR PROCEDURE AND IMAGING

HybridAPC (HAPC) Application

HAPC will be performed in conjunction with ESG in patients in the treatment group. The location is from the level of the incisura all the way to the fundus. The pattern includes 3 rectangular APC ablation zones created on the anterior, greater curvature and posterior surface of the stomach. The HAPC is composed of a submucosal lift followed by ablation. The default setting of the APC is 50 Watts, 1 L/min flow, but it may be adjusted within normal clinical limits dependent on participant anatomy and tissue response. After ablation, ESG will be performed in standard fashion.

Measurement of Gastric Accommodation by Dynamic MRI

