The primary endpoint for power and sample size is durability of plications on repeat endoscopy 6 months after initial procedure with HAPC and ESG and ESG alone. Another primary endpoint for power and sample size is %TBWL at 6 and 12 months.

We plan a 1:1 randomization scheme that allocates to either HAPC ESG (12 patients) or ESG alone (12 patients). Given the pilot nature of this trial, no formal power calculation is feasible or warranted.

Statistical Analysis

Statistical analyses of randomized groups at 6 and 12 months will be performed based on a modified intent-to-treat (mITT) principle for efficacy analyses. Patients randomized but subsequently withdrawn or identified as meeting exclusion criteria prior to intervention (as applied to both the treatment and control arms) will be excluded from the analysis if the reason for exclusion is documented and unrelated to the randomized arm.

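### The mITT set that governs the primary analysis is defined in two conflicting ways, and one of them could let arm-related exits and procedures stopped after HAPC drop out

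*Combined protocol and SAP*

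**What the plan says.** The Statistical Analysis subsection (before 8.2.1) sets a conditional exclusion. "Patients randomized but subsequently withdrawn or identified as meeting exclusion criteria prior to intervention" "will be excluded from the analysis if the reason for exclusion is documented and unrelated to the randomized arm". Anyone who does not meet that condition stays in.

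Section 8.2.3 states that "Modified ITT will be considered the primary approach for all efficacy analyses" and that the set "will include patients who actually received the intervention regardless of adherence to follow-up visits". It puts no condition on why the intervention was not received, and it does not define receipt for a partly completed procedure. The same section defines per-protocol as receiving the procedure and attending at least 80% of follow-up visits. It then allows safety to be evaluated by treatment received, which it labels per-protocol.

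Missing Data adds: "Patients that withdraw/dropout between randomization and intervention are assumed to be missing completely at random". Multiple imputation follows only if withdrawn patients look different or if dropout rates differ substantially between arms.

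On the procedure, HybridAPC (HAPC) Application describes a submucosal lift and ablation, then: "After ablation, ESG will be performed in standard fashion". General Description says: "Control subjects will undergo traditional ESG alone". On accrual, Replacement of withdrawn subjects says: "New patients will be randomized to target accrual of 24 total patients receiving combined HAPC and ESG or ESG alone". Study Setting caps enrollment at 24.

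**The concern.** Both rules are current text, and both claim to define the set used for the 6-month durability endpoint. They disagree on exactly the patients whose absence could depend on the assigned arm.

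The first group exits between randomization and the procedure. That window can last 60 days, and the Randomization section leaves the research team unblinded. The arm-unrelated condition is the plan's only protection against selective exclusion there, and 8.2.3 does not carry it.

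The second group has a procedure that was started but not finished. A stop after ablation and before the first suture can happen only in the HAPC arm, because controls have no ablation step. If such patients leave the set, a failure that arises at the experimental step is not counted against it.

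Safety is a stated objective. If the safety set follows the 80% visit rule, a harm that ends the procedure or the follow-up could also remove the patient in whom it occurred.

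**Working it through.** **Step 1: apply each rule to each kind of patient.**

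| Patient | Statistical Analysis subsection | Section 8.2.3 |
|---|---|---|
| Exits before procedure; reason documented and unrelated to arm | Out | Out |
| Exits before procedure; reason arm-related or undocumented | In | Out |
| Stopped after ablation, before suturing (HAPC arm only) | In: not an exit before the intervention | Not defined; could be out |
| Stopped during suturing (either arm) | In | Not defined; could be out |
| Completed; visits missed | In | In |

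Row 2 is a direct contradiction. Rows 3 and 4 turn on whether receipt means started or completed, which the plan does not say.

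**Step 2: inputs for size.** The plan's only figure is 12 + 12 = 24. It has no power calculation behind it, so there is nothing to reproduce. The abandonment rate and the intact rate are not given; the values below are assumptions. Durability is reduced to intact or not, although the EGD review uses three grades.

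**Step 3: chance of meeting the problem.** The chance of at least one abandoned procedure among 12 HAPC patients is 1 − (1 − p)^12.

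| Assumed p | At least one |
|---|---|
| 2% | 21.5% |
| 5% | 46.0% |
| 10% | 71.8% |
| 15% | 85.8% |

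**Step 4: shift in the HAPC proportion.** Let k of 12 be abandoned and let s be the intact proportion among completers. Excluding the k gives s. Keeping them as not durable gives s(12 − k)/12. The difference is s·k/12.

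- k = 1: 4.2, 5.8 and 7.5 points for s = 50%, 70% and 90%.
- k = 2: 8.3, 11.7 and 15.0 points.
- In counts: 9/11 = 81.8% against 9/12 = 75.0%; 8/10 = 80.0% against 8/12 = 66.7%.

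These figures assume no replacement. If one abandoned patient were replaced, 13 would have started and 12 completed. The difference is then s − 12s/13 = s/13, or 3.8, 5.4 and 6.9 points.

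**Step 5: effect on a test.** Section 8.2.1 names no test for the primary outcome, so two-sided Fisher exact tests serve only as illustration. One completer in the HAPC arm is assumed not intact.

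| Control intact | One abandoned: excluded (10/11) vs kept (10/12) | Two abandoned: excluded (9/10) vs kept (9/12) |
|---|---|---|
| 4/12 | p = 0.009 vs 0.036 | p = 0.011 vs 0.100 |
| 5/12 | p = 0.027 vs 0.089 | p = 0.031 vs 0.214 |
| 6/12 | p = 0.069 vs 0.193 | p = 0.074 vs 0.400 |

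With one abandoned case, the result crosses 0.05 only in the 5/12 row. With two, it crosses in the 4/12 and 5/12 rows.

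**Step 6: safety.** One serious event in the HAPC arm is 1/12 = 8.3% if the patient is kept and 0/11 = 0% if not. Over both arms it is 1/24 = 4.2%. The plan's goal is below 5%, with no denominator stated.

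**Step 7: accrual.** With enrollment capped at 24, a single withdrawal before the procedure leaves 24 − 1 = 23 recipients. The cap and the target of 24 recipients cannot then both hold.

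**The case against.** The strongest reply is that the sentence in 8.2.3 was written to contrast mITT with the 80% visit rule just before it, not to redefine the set. It does not require completion. An ablated patient has had part of the intervention, and read together with the Statistical Analysis subsection, 8.2.3 can keep that patient. This stands as a reading, but not the only one, since the plan elsewhere names the treatment as combined HAPC and ESG. It also does nothing for row 2 of the table.

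A reader might infer that the plan requires a patient stopped after ablation to be dropped and replaced. The documents do not support that. The wording permits exclusion without requiring it. The replacement section concerns withdrawn patients, counts those withdrawn before the procedure towards accrual, and sits beside a cap of 24. Replacement is possible, not established.

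Other points that stand:

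- The abstract presents the submucosal lift as a way to reduce the risk of deep wall injury. Nothing in the documents says such stops are frequent.
- ESG stopped during suturing, or a contraindication at the pre-procedure endoscopy, can occur in either arm.
- Participants are blinded, so voluntary withdrawal is unlikely to depend on arm. The route for arm-related exits is mainly through the unblinded team.
- Adverse events are recorded from procedure day and are to be reported throughout the study. A harm would be recorded even if it left a summary denominator.
- Missing Data already offers multiple imputation. However, it is triggered only by an apparent difference, which is hard to see with 12 per arm.

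**Conclusion.** The conflict between the two definitions is established from the text, and it affects the set used for the primary endpoint. For pre-procedure exits that are arm-related or undocumented, the two rules give opposite answers. For a procedure stopped after ablation, 8.2.3 leaves the answer open, and that loss can arise only in the HAPC arm. The safety wording, read literally, has a parallel gap.

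The consequence is that the results could be biased, not that they are. Each exclusion could be worth roughly 4 to 8 points of HAPC durability, for assumed intact rates of 50% to 90%. Whether any occurs depends on an abandonment rate the documents do not give. The p-values rest on assumed counts and on a test the plan does not name.

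A reader might also infer that one excluded serious event decides whether the 5% safety goal is met. That holds only for the HAPC arm alone (8.3% against 0%). Pooled, one event is 4.2% and stays below 5% either way.

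The pilot label does not remove the point: with 12 per arm, one patient is 1/12, about 8 points of the denominator.

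**What to change.** 1. Put one mITT definition in both the Statistical Analysis subsection and 8.2.3: all randomized patients in whom the study procedure was started (first lift, ablation or suture), analysed in the assigned arm.
2. Keep the condition that a pre-procedure exclusion must be documented and unrelated to arm. To avoid recreating the conflict, state that a pre-procedure exit failing this condition stays in the set, with the outcome handled as missing. Dropping the condition would remove the only safeguard before the procedure starts.
3. Add a full-ITT sensitivity analysis covering every pre-procedure exit, and align Missing Data with it.
4. Use the procedure-started set for safety, without the 80% visit condition. State whether the 5% goal is judged by arm or pooled.
5. In the replacement section, state that a patient whose procedure was started is not replaced. Reconcile the target of 24 recipients with the enrollment cap of 24.
6. Prespecify how an incomplete gastroplasty is scored at week 26 and what counts as incomplete. Durability is undefined without plications, so retention alone does not settle the outcome. Scoring it as not durable should be at least a sensitivity analysis.

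The cost is protocol and SAP wording plus one sensitivity analysis, with no new visits or tests. The durability figures may look slightly less favourable.

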- Improvement in obesity related comorbidities (blood pressure, fasting glucose, HbA1c, lipid panel, liver enzymes) at 6 and 12 months compared to baseline.
- Changes in gastric motility, volume, accommodation, and constructed gastroplasty on MRI at 6 months compared to baseline.
- Changes in gastric emptying evaluated by gastric emptying study at 6 months compared to baseline.
- Changes in liver biochemical panel, and glucose homeostasis parameters at 6 months compared to baseline between the two groups.

Safety

- The incidence, frequency, and severity of adverse events related to treatment with the device will be reported throughout the duration of the study.
- Goal is <5% rate of serious adverse events related to the device or procedure (as determined by the site PI). Serious adverse events will be classified in the Adverse Events table.

Study Setting

The study will be conducted at 1 US center, Mayo Clinic in Rochester, MN. The maximum enrollment will be limited to 24 participants. The expected enrollment period is 6 months.

Subjects

Participants will be adult patients (Ages 21 \geq and \leq 65) with a BMI \geq 30 and \leq 40 kg/m² that meet the eligibility criteria below. All eligibility criteria must be met at the time of randomization.

Inclusion Criteria

1. Age 21-65
2. BMI \geq 30 and \leq 40 kg/m²
3. Willingness to comply with the substantial lifelong dietary restrictions required by the procedure.
4. History of failure with non-surgical weight-loss methods.
5. Willingness to follow protocol requirements, including signed informed consent, routine follow-up schedule, completing laboratory tests, and completing diet counseling.

6. Residing within a reasonable distance from the investigator's office and able to travel to the investigator to complete all routine follow-up visits.
7. Ability to give informed consent.
8. Women of childbearing potential (i.e., not post-menopausal or surgically sterilized) must agree to use adequate birth control methods.

Exclusion Criteria

1. History of foregut or gastrointestinal (GI) surgery (except uncomplicated cholecystectomy or appendectomy).
2. Prior gastrointestinal surgery with sequelae, i.e. obstruction, and/or adhesive peritonitis or known abdominal adhesions.
3. Prior open or laparoscopic bariatric surgery.
4. Prior surgery of any kind on the esophagus, stomach, or any type of hiatal hernia surgery.

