25. Subjects with severe cardiopulmonary disease or other serious organic disease which might include known history of coronary artery disease, myocardial infarction within the past 6 months, poorly controlled hypertension, required use of NSAIDs.
26. Subjects taking medications on specified hourly intervals that may be affected by changes to gastric emptying, such as anti-seizure or anti-arrhythmic medications.
27. Subjects who are taking corticosteroids, immunosuppressants, and narcotics.
28. Symptomatic congestive heart failure, cardiac arrhythmia, or unstable coronary artery disease.
29. Pre-existing respiratory disease such as moderate or severe chronic obstructive pulmonary disease (COPD) requiring steroids, pneumonia, or cancer.
30. Diagnosis of autoimmune connective tissue disorder (e.g. Systemic lupus erythematosus, scleroderma) or immunocompromised.
31. Specific diagnosed genetic disorder such as Prader Willi syndrome.
32. Eating disorders including night eating syndrome (NES), bulimia, binge eating disorder, or compulsive overeating.
33. Known history of endocrine disorders affecting weight such as uncontrolled hypothyroidism.
34. At the discretion of the PI for subject safety
35. If minority inclusion population target of 10% has not been reached by the 90% enrollment mark (example 21 of 24 subjects), the remaining enrollments will be reserved for minority subjects (example 3 of 24 subjects).

TRIAL PROCEDURES

Informed Consent

Prior to being enrolled in the trial, study participants must consent to participate after the nature, scope, and possible risks of the trial have been explained and outlined in an understandable form to them per the requirements of the IRB. Participants are free to withdraw consent at any time.

After reading the Informed Consent Form (ICF) document, the participant must sign and date the latest approved version of the ICF before any study procedures are performed (electronic via compliant system such as DocuSign, or wet-signed copy prepared in Participant Tracking System (Ptrax). A copy of the signed consent document will be accessible for the participant, and the original signed consent form will be retained by the study team.

Where possible, “remote” visits such as via phone or video call will be acceptable across the schedule of events to streamline coordination efforts and adapt to any unexpected conditions such as isolation protocol.

Study Timeline

The study timeline is depicted in Figure 1.

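### The safety set in Section 8.2.3 is called per-protocol, which by the plan's own definition excludes treated patients with poor visit attendance; the wording commits to no set

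*Combined protocol and SAP*

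**What the plan says.** Section 8.2.3 (Secondary Analyses) describes three things in quick succession.

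- The per-protocol set is "defined among as those actually receiving the procedure and making" at least 80% of follow-up visits.
- Modified ITT is the primary approach for efficacy and "will include patients who actually received the intervention regardless of adherence to follow-up visits".
- On safety: "Safety endpoints and adverse events may be evaluated based on treated group (per-protocol".

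No other section names a safety population. Under Statistical Analysis, the comparisons of randomized groups "will be performed based on a modified intent-to-treat (mITT) principle for efficacy analyses", so that set is assigned to efficacy. Under Endpoints, Safety, "The incidence, frequency, and severity of adverse events related to treatment with the device will be reported throughout the duration of the study". The target there reads "Goal is <5% rate of serious adverse events related to the device or procedure (as determined by the site PI"). Neither statement gives a denominator.

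**The concern.** The safety sentence puts two labels on one set. The first, the treated group, suggests everyone who had the procedure. The second, per-protocol, has just been defined with an attendance condition. An analyst who applies the written definition drops treated patients who attended too few visits.

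That exclusion depends on what happens after treatment, and it need not be independent of safety. Participant Retention allows the investigators to withdraw a participant for that participant's protection, and someone with a bad course may stop attending. The patients removed could therefore be those whose events matter most.

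Safety is part of the first study objective and is listed among the secondary endpoints. With at most 24 participants, the reported status of the SAE goal can turn on very few people. Because the sentence is permissive, the choice of set can be made after the data are seen.

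**Working it through.** **Inputs**

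- Visits: the Schedule of Events lists follow-up at weeks 1, 4, 8, 12, 16, 20, 26, 30, 36, 42, 48 and 52, which is 12 visits, or 13 contacts with the post-op call.
- Attendance threshold: 80% (Section 8.2.3).
- Goal: SAE rate strictly below 5% (Endpoints, Safety).
- Patients: Study Setting says "The maximum enrollment will be limited to 24 participants".

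The plan gives no figure of its own to reproduce here.

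**Assumptions**

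- The 80% is counted over the whole 52-week schedule, including for patients who leave early. Section 8.2.3 gives no denominator and does not say whether out-of-window visits count.
- The rate counts patients with at least one related SAE, with both arms pooled. The goal does not specify either.
- 24 patients are treated. The number could be lower, because the section on replacing withdrawn subjects counts pre-procedure withdrawals towards accrual yet also targets 24 treated, while enrollment is capped at 24.
- The documents give no SAE rate or dropout rate, so the cases below are illustrations, not predictions.

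**Step 1: who fails the rule**

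- 0.8 × 12 = 9.6, so at least 10 visits are needed. Two missed: 10/12 = 83.3%, passes. Three missed: 9/12 = 75.0%, fails.
- With the call: 0.8 × 13 = 10.4, so 11 are needed. Two missed: 11/13 = 84.6%, passes. Three missed: 10/13 = 76.9%, fails.
- A patient who attends without a gap and then stops must reach week 42, the tenth visit.

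**Step 2: effect on the goal, 24 treated**

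| Case | All treated | Per-protocol as defined | Goal status |
|---|---|---|---|
| Two SAE patients, one fails the rule | 2/24 = 8.3% | 1/23 = 4.3% | missed to met |
| One SAE patient stays in, four event-free patients fail | 1/24 = 4.2% | 1/20 = 5.0% | met to missed |
| One SAE patient, who fails | 1/24 = 4.2% | 0/23 = 0% | met both ways |
| Three SAE patients, one fails | 3/24 = 12.5% | 2/23 = 8.7% | missed both ways |

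**Step 3: fewer treated**

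- The first change also occurs with 23 treated (2/23 = 8.7% to 1/22 = 4.5%) and with 22 (2/22 = 9.1% to 1/21 = 4.8%).
- It does not occur with 21 (2/21 = 9.5% to 1/20 = 5.0%).
- With 20, it needs only one SAE patient, who fails the rule (1/20 = 5.0% to 0/19 = 0%).
- The reverse change needs 3, 2 or 1 event-free patients failing the rule with 23, 22 or 21 treated, since each case ends at 1/20.

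**Step 4: precision**

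Exact (Clopper-Pearson) 95% intervals are 1.03% to 27.00% for 2/24 and 0.11% to 21.95% for 1/23. They overlap almost entirely.

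**The case against.** The best defense is that per-protocol is loose shorthand for as treated. The paragraph first compares randomized groups and then turns to the treated group, so the contrast may concern how patients are grouped, not who is left out. The commitment under Endpoints that events will be reported carries no attendance condition, which favors the inclusive reading. This is a plausible account of the intent. It does not settle the matter, because the term was given a different meaning in the same paragraph and no section restates it.

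Failing the rule may also be uncommon. Remote "visits such as via phone or video call will be acceptable across the schedule of events", and the plan promises efforts to retain patients. These make failure less likely but do not exclude it.

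The change in goal status is narrow as well. With 22 to 24 treated, moving from missed to met by losing one SAE patient requires exactly two SAE patients; at 24, the reverse requires four event-free patients to drop out of the set. The goal is descriptive, with no test attached. These limits stand, and they confine the point to the reported summaries.

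A reader might infer that the plan hides adverse events, weakens the stopping rules or biases the SAE rate downward. The documents do not support this. Events are still collected at every visit, reported to the IRB, and counted by the investigator against the stopping rules without reference to an analysis set. The direction of any shift in the rate is not fixed.

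**Conclusion.** The point holds as a defect in specifying the safety population, and it should be corrected before analysis. The only term the plan defines for this set carries an attendance condition that does not belong in a safety summary, and the permissive wording leaves the choice open.

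What is affected is the summary rates and whether the under-5% goal is reported as met. The strength of the evidence hardly changes, as the intervals show. The three-missed-visits threshold depends on counting over the full schedule, and the worked cases depend on pooling the arms, counting patients rather than events, and the assumed number treated. The inconsistency in the text depends on none of these.

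**What to change.** Replace the safety sentence in Section 8.2.3 with: *Safety endpoints and adverse events will be evaluated in all patients in whom the study procedure was begun, grouped by procedure received, regardless of follow-up visit attendance.* This removes both the permissive verb and the per-protocol label. If grouping by procedure received was intended all along, the change only writes that down.

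The cost is one sentence and no new data. The downside is that the SAE rate may look less favorable. Patients who leave early also contribute shorter follow-up, so its length should be shown alongside the rates.
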